- iv. Prior to acceptance for surgery, patients seen in the bariatric clinic must undergo psychological assessment and complete a supervised comprehensive lifestyle program. Please refer to ⁴⁶ for details.
- v. Female subjects (randomized to study drug) who are sexually active and able to become pregnant, must agree to use birth control methods for the duration of the study

c) Exclusion Criteria:

- i. Prior use of glucose lowering medication in the 3 months prior to screening.
- ii. A fasting glucose $\geq 126\text{mg/dl}$ or an HbA1c $\geq 6.5\%$ will be taken as evidence of type 2 diabetes and therefore patients will be deemed ineligible for participation.
- iii. Prior abdominal surgery other than those that would not affect glucose metabolism, i.e., cholecystectomy, appendectomy, C-section or hysterectomy.
- iv. Pregnancy or active consideration of pregnancy during the period of study. Subjects will be discontinued if they become pregnant during the study.
- v. Hypersensitivity to liraglutide or any product components.
- vi. Personal or family history of medullary thyroid carcinoma or Multiple Endocrine Neoplasia type 2 in those who will undergo sleeve gastrectomy
- vii. Prior history of pancreatitis, cholelithiasis or cholecystitis.
- viii. Concurrent use of insulin or any other GLP-1 receptor agonist.
- ix. Active, severe psychiatric disease
- x. Pregnancy or breastfeeding

d) Surgery: Subjects will then undergo the surgery to which they had been assigned on clinical grounds. At present there are no clear guidelines in this regard and a patient is assigned to a bariatric surgical procedure based mainly on clinical factors. Clinical factors considered include the presence of specific obesity-related comorbid diseases and body mass index. Also considered are the patient's psychological complexity, social situation, and a patient's particular preference. A prior history of severe gastro-esophageal reflux is a relative contraindication to SG. **Note that the study team will play no role in that decision other than to ensure that participants in either group are matched for age, sex and BMI.** At Mayo Clinic, Rochester the standard protocol is to see patients back for care at 3, 6 and 12 months and then annually after bariatric surgery.

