e) Randomization: Subjects undergoing SG will be randomized (1:1) at the time of the 3 month visit after bariatric surgery. A double-blind design will be utilized. Liraglutide will be started at 0.6 mg SUBQ daily for 1 week. Subsequently, Liraglutide will be increased by 0.6 mg SUBQ daily on a weekly basis till the maintenance dose of 3.0 mg/day is reached. The placebo dose will also be titrated in a similar fashion. The study medication will be dispensed by the research pharmacy which will handle randomization and ensure that blinding is maintained. SG subjects will return to the CRTU for dispensing of study drug at standard follow-up visits (months 6, 12, 24, 36) and also at months 18 and 30. Subjects undergoing RYGB will return to the CRTU at standard follow up visits, months 3, 6, 12, 24, 36. Recruitment will continue till 50 subjects after SG are randomized and 25 subjects after RYGB are enrolled.

f) Study Visits: These will be timed to coincide with the standard follow-up visits at 3, 6, 12, 24 and 36 months after bariatric surgery. In addition to a history and physical examination, blood will be collected for creatinine, fasting glucose, HbA_{1c}, fasting lipid profile and hepatic panel, and urine collection to exclude pregnancy in females of child bearing potential. Supine and standing blood pressure will also be measured as well as body composition using DXA (at months 12, 24 and 36). Habitual activity levels⁴¹, bowel symptoms⁴², Stunkard's Eating Inventory⁴³, The Weight Efficacy Life-Style Questionnaire⁴⁴ & Eating and Weight Patterns-Revised⁴⁵ will be assessed. Collected data will include height, weight, blood pressure, pulse rate, medications used, and adverse events. During clinic visits, as per standard practice, subjects will meet with a dietitian and with a behavioral psychologist. Compliance will be assessed using an electronic record of food intake. The psychologist will use motivational enhancement and behavior change techniques to promote compliance with the dietary guidelines⁴⁷. In addition, to ensure compliance with instructions to increase physical activity, which will be reiterated at each visit, we will gather information about daily step counts from step-counters or smartphones.

g) Telephone follow up: The study coordinator will schedule monthly calls with each subject (or more frequently if necessary) to rapidly identify problems and help ensure compliance.

h) Early Termination

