For any patient enrolled in the study, the study participation will be concluded after the last visit at month 36, or at early termination. Should any patients withdraw or be withdrawn from the study, all of the Early Termination assessments should be completed before early termination, if possible, including; blood collection for creatinine, fasting glucose, HbA_{1c}, fasting lipid profile, hepatic panel, and urine collection to exclude pregnancy in females of childbearing potential. Supine and standing blood pressure will also be measured as well as body composition using DXA. Habitual activity levels, bowel symptoms, Stunkard's Eating Inventory, The Weight Efficacy Life-Style Questionnaire & Eating and Weight Patterns-Revised will be assessed. Collected data will include height, weight, blood pressure, pulse rate, medications used if applicable, and adverse events.

i) Power Calculation: See detailed power calculations below.

j) Adverse Event Monitoring: The most common adverse reactions associated with liraglutide use are nausea, dizziness, abdominal pain, increased lipase, hypoglycemia, diarrhea, constipation, vomiting, headache, decreased appetite and dyspepsia. Acute pancreatitis has been associated with liraglutide use. Relevant symptoms will be screened for at the time of routine follow-up as well as telephone follow-up.

1) Interpretation: We will accept our primary hypothesis that administration of 3.0mg liraglutide to participants after SG increases weight loss compared to placebo if after unblinding, the liraglutide group has significantly greater weight-loss from baseline

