compared to the SG + placebo group. Similarly, we will reject our 2° (i) hypothesis if the weight loss observed in participants who undergo SG and receive Liraglutide does not differ from that after RYGB. Such a conclusion would support a role of GLP-1 in the weight loss achieved (and maintained) after RYGB. The questionnaires collected over the duration of the study will be utilized to help generate hypotheses related to food intake as it is affected by liraglutide use after SG compared to placebo. As before, we will determine whether the addition of liraglutide to SG improves effects of SG on cholesterol and blood pressure ¹⁵. If this indeed the case, we will accept our 2° hypothesis (ii). If the high GLP-1 concentrations observed after RYGB modulate appetite and food intake as suggested by our preliminary data (Fig. 1), we would expect weight loss after RYGB to also lower cholesterol and blood pressure. We will reject our 2° (iii) hypothesis if the blood pressure and LDL-cholesterol lowering observed in participants who undergo SG and receive Liraglutide does not differ from that after RYGB.

STATISTICAL CONSIDERATIONS:

Using JMP® Pro 11.2.1 (SAS Institute) for the power calculation we established the following: -

In a prior experiment¹⁵ we observed an overall [mean value \pm (SD)] of % weight change after RYGB = $-26.1 \pm (8.7)$ at 1 year. Assuming similar variation, 25 subjects who complete the study in each group would provide approximately 80% power (at a 2-sided 0.05 α level), to detect a 7.0% difference in weight change between SG + treatment vs. SG + placebo. An intention to treat analysis will be undertaken.

In another, as yet unpublished experiment, 12 subjects studied before and 4 weeks after RYGB lost 11.0 ± 3.4 Kg within 4 weeks. Assuming similar variation, 25 subjects per group would provide approximately 80% power (at a 2-sided 0.05 α level), to detect a difference of a 2.7 Kg in weight between groups.

Schauer et al.¹⁴ observed an overall [mean value \pm (SD)] of weight change after RYGB = $-29.4 \pm (8.9)$ Kg. Assuming similar variation, 25 subjects per group would provide approximately 80% power (at a 2-sided 0.05 α level), to detect a 7.2kg between-group difference.

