 - termination of the study.Any studies that are suspended or terminated will be promptly reported to the sponsor that has provided funding for the study and/or to the FDA if the study involves an IND or an IDE.
11. All other events not requiring suspension or termination shall be reported to the FDA through the normal reporting channel (notification from the investigator to the sponsor to the FDA).
12. The minutes generated by the Subcommittee are approved by the convened IRB. The convened IRB will generate a subsequent minute excerpt only if additional action is taken (i.e., approval of revised consent form, revisions to the protocol, etc.).

Follow-up of Adverse Events

We will provide adequate medical care to the study subject for any study-related adverse events, including clinically significant laboratory values related to the study regardless of their insurance status. All adverse events classified as serious or severe or possibly/probably related to the trial product will be followed until the subject has recovered and all queries have been resolved.

Pregnancy

Study subjects will be instructed to notify the sponsor-investigator immediately if they become pregnant. We will report to Novo Nordisk any pregnancy occurring during the trial period. Further participation in the study will be discontinued but telephone follow-up will continue to monitor the pregnancy and its outcome. The investigator will report to Novo Nordisk information about the pregnancy, pregnancy outcome, and health of the newborn infant(s), as well as AEs in connection with the pregnancy, and AEs in the foetus and newborn infant. Pregnancy complications will be recorded as adverse event(s). If the infant has a congenital anomaly/birth defect this will be reported as a serious adverse event.

[name] will be responsible for reporting of all adverse events including serious adverse events (SAE), suspected unexpected serious adverse reactions (SUSARs), serious adverse drug reactions (SADRs) to the competent authority and IRB based upon federal regulations and local IRB policies.

[name] will report to Novo Nordisk all SAEs, SUSARs, and SADRs at the same time such events are reported to regulatory authorities or within 15 days from the PI becoming aware of such adverse events, whichever comes first.

State that the sponsor-investigator will collect the following information at minimum for each of these events:

1. Study name
2. Patient identification (e.g., initials, sex, age)

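### An intention-to-treat analysis is promised, but no weights are planned after early termination and no rule covers leavers; the 80% power also fails if only 50 sleeve patients are randomised

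*Combined protocol and SAP*

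**What the plan says.** Section h) Early Termination sets the end of data collection: "the study participation will be concluded after the last visit at month 36, or at early termination". It adds one exit assessment: "Should any patients withdraw or be withdrawn from the study, all of the Early Termination assessments should be completed before early termination, if possible". That assessment includes weight: "Collected data will include height, weight, blood pressure, pulse rate, medications used if applicable, and adverse events".

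Statistical Considerations gives the analysis set in one sentence, "An intention to treat analysis will be undertaken", directly after a power statement for completers: "25 subjects who complete the study in each group would provide approximately 80% power". The target is a 7.0-point difference in percentage weight change, with SD 8.7 taken from gastric bypass patients at 1 year.

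The sample size appears in two forms. The opening of Research Design and Methods enrols 60 SG patients and allows a loss of 5 per group, leaving 25. Section a) Subjects gives 50 SG patients, and section e) Randomization continues recruitment until 50 SG patients are randomised, 1:1, at the month 3 visit.

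Under section d) Surgery, standard care at the site is to "see patients back for care at 3, 6 and 12 months and then annually after bariatric surgery". Section f) Study Visits times the study visits to coincide with these.

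**The concern.** An intention-to-treat analysis needs either an outcome for every randomised patient or a stated assumption in place of the missing ones. The plan has neither. It provides for no study weight after early termination. It names no analysis model, missing-data method, use for the exit weight, or time point for the primary endpoint.

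It also describes no status for a patient who has stopped study drug but is still followed. The one case it spells out is pregnancy, where participation ends: "Further participation in the study will be discontinued but telephone follow-up will continue to monitor the pregnancy and its outcome". For other patients who stop drug, the path is not stated.

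This matters because drug starts at month 3 and follow-up runs to month 36, so an exit weight may come from a very different point on the weight curve than the final visit. Section j) Adverse Event Monitoring lists nausea, vomiting, diarrhea, abdominal pain and dyspepsia among the common reactions to liraglutide, so the rate of leaving, and the reasons for it, could differ by arm. Randomisation does not protect a contrast among those who remain.

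The power statement has a related weakness. It describes completers given the full 7.0-point effect, which is not the contrast an intention-to-treat analysis estimates once some patients are off drug.

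**Working it through.** **Inputs.** From Statistical Considerations: difference 7.0, SD 8.7, two-sided alpha 0.05, 25 completers per arm. From the opening of Research Design and Methods: 60 SG patients (30 per arm), 5 lost per group. From section e): 50 SG randomised (25 per arm).

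**Method.** Two-sample t test with n per arm. Standard error = SD × √(2/n), noncentrality = difference / standard error, df = 2n − 2, and power from the noncentral t distribution.

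**1. The plan's own figure.** n = 25: standard error = 8.7 × √(2/25) = 2.461; noncentrality = 7.0/2.461 = 2.845; power 79.6%. The stated 80% reproduces. The inflation is also correct: 25/(1 − 5/30) = 30 per arm.

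**2. Fifty randomised, then 5 lost per arm.** n = 20: standard error = 8.7 × √(2/20) = 2.751; noncentrality = 7.0/2.751 = 2.544; power 69.8%. The difference detectable with 80% power rises from about 7.0 to 7.9 points.

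**3. All randomised patients measured, 5 liraglutide patients off drug.** If they retain a share r of the effect (an assumption), the average difference is 7.0 × [1 − (5/n)(1 − r)].

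| Randomised per arm | Effect retained | Difference | Power |
|---|---|---|---|
| 30 | none | 7.0 × 25/30 = 5.83 | 72.4% |
| 30 | half | 7.0 × (1 − 2.5/30) = 6.42 | 80.2% |
| 25 | none | 7.0 × 20/25 = 5.60 | 60.6% |
| 25 | half | 7.0 × (1 − 2.5/25) = 6.30 | 70.8% |

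The SD is held at 8.7. Adding the extra spread from mixing on-drug and off-drug patients lowers each figure by 2.1 points or less (72.4% becomes 70.5%).

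**4. Size of a possible bias (illustration only).** No true effect, SD 8.7, 30 per arm, 5 leaving each arm, completers compared. Leaving is tied to poor weight loss in the liraglutide arm and is random in the placebo arm. The documents give no dropout by arm or reason, so the strength of the tie is assumed. Results are from simulation.

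| Correlation of leaving with outcome | False benefit (points) | Type I error |
|---|---|---|
| 0.2 | 0.5 | about 5% |
| 0.5 | 1.3 | about 9% |
| 1 (the five poorest responders leave) | 2.5 | about 21% |

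If leaving is tied to outcome equally in both arms, the average shift is zero, with type I error about 6% at correlation 0.5 and just under 10% at correlation 1.

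**The case against.** The strongest reply is that the plan does not discard anyone. Intention to treat is promised, weight is recorded at every visit attended, and an exit weight is planned. Those data could support a repeated-measures or imputation analysis of all randomised patients. This is fair. A reader might infer that the analysis must become a completer comparison, but no section excludes non-completers. What remains is that the plan does not say which analysis will be done, and each option carries its own assumption about weights after exit.

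The trigger in section h) is withdrawal from the study, so a reader might also infer that stopping drug ends data collection. The documents do not say so. They do not say the opposite either, and pregnancy is the only case described.

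On power, basing the sample size on completers and enrolling 30 to keep 25 is correct practice, so counting completers does not by itself overstate power. If patients off drug retain half the effect, 30 per arm still gives 80.2%.

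On bias, reading the 21% as a forecast would be wrong. It needs the five poorest responders to leave one arm while placebo losses are random. Patients leaving for vomiting or decreased appetite could be losing more weight than average, which would reverse the sign.

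Finally, SG patients return for drug "and also at months 18 and 30", visits that are absent from the assessment schedule in section f). Weighing them then would add little (an estimated 1% reduction in month 36 variance), so it is not part of this point.

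**Conclusion.** The point holds as a gap between the promised analysis and the planned data. As written, patients who leave have no later weights, and no stated assumption takes their place. Bias is a risk of unknown sign and size. The range of 0.5 to 2.5 points only shows what one-sided, outcome-related leaving of 5 in 30 could do.

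The firmest basis for the power concern is the conflict over sample size. The stated 80% stands if 60 SG patients are randomised and 5 per arm are lost. It drops to about 70% if 50 are randomised and 5 per arm are then lost. If 60 is the number enrolled before surgery and 50 the number randomised at month 3, the whole allowance is spent before randomisation.

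For the intention-to-treat contrast with 5 liraglutide patients off drug, power is 72% to 80% with 30 per arm and 61% to 71% with 25. These ranges assume that none or half of the effect is retained, and that the 1-year gastric bypass SD applies to SG patients at whichever time point is chosen. The documents do not name one.

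**What to change.** - In section h), define stopping study drug separately from leaving the study. Keep all randomised patients on the existing weight schedule to month 36 unless they withdraw consent, and reconcile the pregnancy provision with this wording. This concerns data collection only and implies nothing about when treatment should stop.
- Ask consent to use weights from standard-care clinic visits, where available, for patients who leave study procedures. Former participants may not attend every visit, so this will reduce missing data without removing it.
- In Statistical Considerations, name the primary time point. Specify an analysis of all randomised patients as assigned, using a repeated-measures model on all weights, including off-drug and exit weights. Add a sensitivity analysis for missing data.
- Reconcile 60 with 50 SG patients across the opening of Research Design and Methods, section a) and section e), and say whether the loss of 5 per group falls before or after randomisation.
- Restate power for the intention-to-treat analysis as a range, with its retained-effect assumption, beside the completer figure.

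The cost is protocol and consent wording, retrieval of routine clinic weights, and a less favourable stated power. Because study visits already coincide with standard care, extra visits should seldom be needed.

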The study will only be initiated after it has completed review and approval by the Mayo Institutional Review Board (the IRB). Scientific review will initially be conducted by the Endocrine Research Unit and by the Clinical Research Trials Unit, prior to ethical approval by the IRB which will also approve all patient contact material, advertising and consent forms. The latter will be utilized to ensure informed, written consent is obtained at the time of screening where they will meet the principal investigator or a member of the team to ensure that participants meet entry criteria for the study, understand the risks of participation and the goals of the study.

All Mayo IRB approved studies adhere to the Declaration of Helsinki and are conducted in accordance with ICH good clinical practice (GCP) guidelines. [name] in his role as sponsor-investigator will comply with all these guidelines as well as the other applicable regulatory and legal guidelines during study conduct and when obtaining and documenting informed consent.

The nature of the information obtained for the purposes of the study will be explained in detail to each participant at the time of screening. Specifically, none of this information will become part of the medical record and cannot impact the availability and nature of care or access to healthcare. All information will be stored anonymously in the database and only the PI or one of his designates will have access to the data.

Study Hypothesis: Agonism of the GLP-1 receptor by Liraglutide 3mg will increase weight loss and lower blood pressure and LDL-cholesterol compared to placebo after sleeve gastrectomy.

1° Endpoint: Liraglutide administration (3mg daily) to participants after SG produces significantly greater weight loss from baseline compared to that observed in the group after sleeve gastrectomy who receive placebo.

2° Endpoints:

[figure not shown]
- i. Liraglutide administration (3mg daily) to participants after SG produces will achieve weight loss that is inferior to that achieved by RYGB.
- ii. Greater numbers of participants after SG will have an LDL \leq 100mg/dL and a systolic blood pressure \leq 130mmHg results when receiving Liraglutide (3mg daily) compared to placebo.
- iii. Liraglutide administration (3mg daily) to participants after SG produces blood pressure and LDL-cholesterol lowering that is inferior to that achieved by RYGB.

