We propose enrolling 60 non-diabetic adults scheduled for SG and 30 patients undergoing RYGB. Patients scheduled for SG will be randomized to receive Liraglutide (3mg daily) in a double-blind, randomized, placebo-controlled fashion (randomized in a 1:1 ratio). All participants will be followed longitudinally with serial measurement of outcome variables (weight, blood pressure, lipid profile, activity and satiety) over a three year period. Our power calculations suggest that 25 patients per group will be sufficient to accomplish our goals even with a loss of 5 subjects per group to follow up.

Bariatric Sx	2008		2009		2010		2011		2012		2013	
	ND	DM										
RYGB	107	46	166	70	160	63	207	83	184	64	210	59
AGB	9	0	27	0	10	0	34	4	8	2	3	1
SG	0	0	25	0	32	10	62	29	78	25	102	36

Table 1: Total numbers of laparoscopic surgeries performed as 1st procedure at Mayo Clinic. AGB = Adjustable Gastric Banding; ND = Non-diabetic; DM = Diabetic patients.

a) Subjects: A total of 75 patients will be recruited from the Nutrition Clinic at Mayo Clinic Rochester prior to undergoing bariatric surgery. Of these 25 will be scheduled for RYGB while the remainder (50) are scheduled for SG. Healthy status will indicate that the participant has no known active systemic illnesses or active macrovascular disease. To be eligible subjects must be willing to participate in all the studies outlined. **Baseline Visit:** Subjects will provide written informed consent. To ensure they are healthy, subjects will undergo a history and physical examination including supine and standing blood pressure; blood collection for complete blood count, HbA_{1c}, fasting lipid profile, electrolytes, hepatic panel and urine collection to exclude pregnancy in females of child bearing potential. Habitual activity levels⁴¹, and bowel symptoms⁴² will be assessed.

BMI $\geq 35 \text{ kg/M}^2$ in the presence of at least one weight-related comorbid condition including hypertension, obstructive sleep apnea or dyslipidemia. Alternatively, a BMI $\geq 40 \text{ kg/M}^2$ without comorbid conditions is deemed to confer eligibility for bariatric surgery at the Mayo Clinic.

ii. Age will be between 20 and 65 years of age.

- iii. Subjects will have no active physical illness which will interfere with mobility or weight loss after bariatric surgery.

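### Adjust the primary sleeve-gastrectomy comparison for pre-dose month-3 weight loss: a low-cost precision gain whose size depends on a correlation the plan does not give

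*Combined protocol and SAP*

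**What the plan says.** **Timing.** Under a) Subjects, "patients will be recruited from the Nutrition Clinic at Mayo Clinic Rochester prior to undergoing bariatric surgery". The Baseline Visit described there is the only visit with that name. Section d) Surgery continues: "Subjects will then undergo the surgery to which they had been assigned on clinical grounds". Section e) Randomization states: "Subjects undergoing SG will be randomized (1:1) at the time of the 3 month visit after bariatric surgery". It then describes the start of study drug. Its list of return visits for dispensing begins at month 6, so a first dose at month 3 is a reasonable inference rather than stated text.

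**Data.** Of the study visits, f) Study Visits says: "These will be timed to coincide with the standard follow-up visits at 3, 6, 12, 24 and 36 months after bariatric surgery". It adds: "Collected data will include height, weight, blood pressure, pulse rate, medications used, and adverse events". Under h) Early Termination, "the study participation will be concluded after the last visit at month 36, or at early termination". Weight is therefore available at month 3 and at four later visits (months 6, 12, 24 and 36).

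**Primary comparison.** The 1° Endpoint is that liraglutide after SG "produces significantly greater weight loss from baseline compared to that observed in the group after sleeve gastrectomy who receive placebo". Section 1) Interpretation accepts the hypothesis if, after unblinding, "the liraglutide group has significantly greater weight-loss from baseline" relative to the placebo arm. Neither place defines baseline, names a visit or chooses between % and kg.

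**Analysis.** Statistical Considerations gives about 80% power for a 7.0% difference, using a 1-year SD of 8.7 after RYGB, 25 completers per group and a two-sided 0.05 level. It also gives power in kg. The only statement on analysis is that it will be by intention to treat. No model or covariate is named.

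**The concern.** If baseline is pre-surgery, each patient's outcome is the sum of the loss before randomisation and the loss after it. The drug can act only on the second part. Differences between patients in the first part add noise to the arm comparison unless the analysis removes them. The value needed to do so is already collected, and the trial is small, with planned power of only about 80%.

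Pre-specification is also at stake. Once the data are unblinded, the plan would allow unadjusted loss from surgery, loss from month 3, or an adjusted difference. With month-3 loss as covariate, part of that choice disappears. The treatment contrast is the same whether the outcome is loss from pre-surgery or loss from month 3, provided both are expressed as a percentage of pre-surgery weight.

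**Working it through.** **Inputs from Statistical Considerations.** n = 25 completers per arm; two-sided 0.05. On the % scale: difference 7.0, SD 8.7 (1 year after RYGB), SD 3.0 (12-week diet experiment). On the kg scale: difference 7.2, SD 8.9 (after RYGB), SD 4.2 (12-week diet experiment).

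**Assumed.** The correlation r between month-3 and final % loss is not in the documents, so a range is shown.

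**1. The plan's own figure.** SE = 8.7 × √(2/25) = 2.461. Noncentrality = 7.0/2.461 = 2.84. Noncentral t with 48 df gives power of 79.6%, which agrees with the stated figure of about 80%. The difference detectable with 80% power is 7.04 points.

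**2. One-covariate ANCOVA.** Residual SD = 8.7 × √(1 − r²). The SE is multiplied by √(1 + 1/46) to allow for chance imbalance in the covariate, and the test has 47 df.

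| r | Power |
|---|---|
| 0 | 78.7% |
| 0.1 | 79.1% |
| 0.2 | 80.3% |
| 0.3 | 82.4% |
| 0.345 | 83.6% |
| 0.4 | 85.3% |

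Adjustment breaks even with the unadjusted 79.6% at about r = 0.15. A simulation of fitted ANCOVAs gave 83.5% at r = 0.345.

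**3. Illustrative values of r.** Suppose weight change after month 3 is uncorrelated with loss up to month 3. Then r is the month-3 SD divided by the final SD.
- % scale: r = 3.0/8.7 = 0.345. Residual SD = 8.7 × √(1 − 0.119) = 8.17. SE = 8.17 × √(2/25) = 2.31, or 2.33 after the imbalance factor. Power goes from 79.6% to 83.6%, and the detectable difference from 7.04 to 6.68 points.
- kg scale: r = 4.2/8.9 = 0.47. Residual SD = 7.85. Power for 7.2 kg goes from 80.0% to 88.2%.

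**4. Change from month 3 as the alternative.** SD = √(8.7² + 3.0² − 2r × 8.7 × 3.0), with no covariate. At r = 0 the SD is 9.20 and power 75.0%; at r = 0.1, 8.91 and 77.7%; at r = 0.2, 8.62 and 80.4%; at r = 0.345, 8.17 and 84.4%. It does slightly better than ANCOVA at r = 0.345 but can lose 79.6 − 75.0 = 4.6 percentage points, against 79.6 − 78.7 = 0.9 for ANCOVA.

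**5. Fewer completers.** Section e) Randomization stops recruitment once 50 SG patients are randomised, and the design overview allows for losing 5 per group. If both apply, 25 − 5 = 20 per arm complete. SE = 8.7 × √(2/20) = 2.75 and power is 69.8% unadjusted. With the covariate at r = 0.345 (37 df, factor √(1 + 1/36)) it is 74.0%.

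**6. A larger final SD (assumption).** With a month-3 SD of 3.0 and the step 3 assumption, a final SD of 10 gives 67.9% to 71.0%, and a final SD of 12 gives 52.4% to 54.2%.

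**The case against.** The strongest case against is that nothing here is an error. Randomisation balances month-3 loss in expectation, the unadjusted test is valid, and its stated power is correct. The covariate's value rests on an unknown correlation, and below about r = 0.15 it costs a little power. All of that stands, and it is why the point is an improvement rather than a correction. A reader might infer that measuring from a pre-randomisation baseline biases the comparison or makes the power claim wrong. The documents do not support either inference.

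A reader might also infer that a rise to 83–84% follows from the plan's own SDs. It does not. SDs alone imply no gain, and a correlation has to be assumed. The same construction gives 83.6% on the plan's % figures and 88.2% on its kg figures. The SDs come from different cohorts, neither of them SG patients. The cited titles place the source studies in people with diabetes, whom this trial excludes. Dividing one cohort's SD by another's does not estimate a within-patient correlation, so both results are illustrations only.

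A further objection is that the choice of visit and its SD can matter more than the covariate. Step 6 bears this out: an SD of 12 would lower unadjusted power by 79.6 − 52.4 = 27.2 points. The visit should therefore be fixed together with the covariate. This does not remove the reason to adjust.

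**Conclusion.** The point holds as a cheap improvement. On the natural reading of baseline, the planned comparison carries pre-randomisation variation that an already collected weight could remove. For r between 0 and 0.4 the change in power runs from −0.9 to +5.7 percentage points (78.7% to 85.3%, against 79.6%), and it is positive above about r = 0.15. The downside is small and bounded; the upside cannot be fixed from the documents.

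The range assumes 25 completers per arm, an SD of 8.7, a difference of 7.0 points and a month-3 weight taken before dosing. The 25 completers are not assured: the design overview gives 60 SG patients, a) Subjects gives 50, and e) Randomization stops at 50 randomised. The pre-surgery meaning of baseline is also a reading, though a strong one.

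**What to change.** Before unblinding, add to the analysis plan:

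1. Baseline is the pre-surgery Baseline Visit, and the primary outcome is % weight change from that visit.
2. One named primary visit. The SD of 8.7 is a 1-year value, so the 80% figure applies to month 12; if month 36 is chosen, restate power with an SD for that visit.
3. The primary SG liraglutide versus placebo analysis is an ANCOVA, or a mixed model with the contrast at the primary visit, with treatment and month-3 % weight loss as terms. The month-3 weight is to be recorded before the first dose.
4. Change from month 3 is reported as supportive only.
5. The SG versus RYGB comparisons (secondary endpoints i and iii) are not adjusted for month-3 loss, because early loss is part of the surgical difference being compared.

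The cost is wording and one degree of freedom, at most 0.9 percentage points of power if r = 0. No visit or measurement is added. The SG recruitment figures should be reconciled at the same time, since every power figure depends on the number of completers.
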